4.5.4.3 Lenalidomide

Dose adjustments, as summarized below, are recommended for the management of NCI CTCAE Grade 3 and 4 toxicities for thrombocytopenia, neutropenia or other toxicities that are judged by the investigator to be related to lenalidomide. Information in Table 4.5.4.3-1 and Table 4.5.4.3-2 is based on current standard of clinical practice.

Table 4.5.4.3-1: Treating Thrombocytopenia Related to Lenalidomide

When Platelet Counts:	Recommended Course
Fall to < 30,000/mm ³	Interrupt lenalidomide treatment; follow complete blood counts weekly.
Return to ≥ 30,000/ mm ³	Resume lenalidomide at 15 mg, Days 1 - 21, once daily.
For each subsequent drop < 30,000/ mm ³	Interrupt lenalidomide treatment.
Return to ≥ 30,000/ mm ³	Resume lenalidomide at 5 mg less than previous dose, Days 1 - 21, once daily. Do not dose below 5 mg.

Table 4.5.4.3-2: Treating Neutropenia Related to Lenalidomide

When Neutrophil Counts:	Recommended Course
Fall to < 1000/ mm ³	Interrupt lenalidomide treatment, add G-CSF; ^a follow complete blood counts weekly.
Return to ≥ 1000/ mm ³ and neutropenia is the only toxicity	Resume lenalidomide at 25 mg, Days 1 - 21, once daily.
Return to ≥ 1000/mm ³ and if other toxicity	Resume lenalidomide at 15 mg, Days 1 - 21, once daily.
For each subsequent drop < 1000/ mm ³	Interrupt lenalidomide treatment.
Return to ≥ 1000/ mm ³	Resume lenalidomide at 5 mg less than previous dose, Days 1 - 21, once daily. Do not dose below 5 mg.

In case of neutropenia, consider the use of growth factors in subject management.

^a G-CSF = Granulocyte Colony-Stimulating Factor

Lenalidomide Dose Adjustments in Subjects with Renal Impairment

Since lenalidomide is primarily excreted via the kidney, adjustments to the dose of lenalidomide are provided based on the lenalidomide country prescribing information. The regimen of 21-day dosing every 28 days remains the same despite the dose reductions described below.

Table 4.5.4.3-3: Lenalidomide Dose Adjustments in Subjects with Renal Impairment

Creatinine Clearance (CrCl):	Recommended Course
Moderate renal impairment (30 ≤ CrCl < 60 mL/min)	10 mg, every 24 hours
Severe renal impairment (CrCl < 30 mL/min, not requiring dialysis)	15 mg every 48 hours
End Stage Renal Disease (CrCl < 30 mL/min, requiring dialysis)	5 mg once daily. On dialysis days, dose should be administered following dialysis

Source: Lenalidomide USPI

Dose Adjustments During Treatment for Other Grade 3 and 4 Toxicities

Angioedema, Grade 4 rash, exfoliative or bullous rash, Stevens-Johnson syndrome or toxic epidermal necrolysis requires permanent discontinuation of lenalidomide. For Grade 2 - 3 skin rash judged to be related to lenalidomide interruption or discontinuation should be considered.

For other Grade 3 and 4 toxicities judged to be related to lenalidomide, hold treatment and restart lenalidomide at the next lower dose level when toxicity has resolved to ≤ Grade 2.

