- d) Hemoglobin $<$ 8 g/dL. Qualifying laboratory value must occur at most recent measurement prior to randomization and must be no more than 14 days prior to randomization. No transfusions are allowed within 72 hours prior to qualifying laboratory value.
- e) Total bilirubin \geq 2 x ULN or direct bilirubin \geq 2.0 mg/dL.
- f) AST or ALT \geq 3 x ULN.
- g) Creatinine clearance (CrCl) $<$ 30 mL/min measured by 24-hour urine collection or estimated by the Cockcroft and Gault formula:
Female CrCl = (140 - age in years) x weight in kg x 0.85 / 72 x serum creatinine in mg/dL
Male CrCl = (140 - age in years) x weight in kg x 1.00 / 72 x serum creatinine in mg/dL

4. Prior Therapy or Surgery

- a) Administration of systemic chemotherapy, biologics, immunotherapy, clarithromycin or any investigational agent (therapeutic or diagnostic) for multiple myeloma except bisphosphonate therapy within 3 weeks prior to randomization.
- b) Treatment with plasmapheresis within 4 weeks prior to randomization.
- c) Steroids within 3 weeks of randomization, except:
 - i) short course (of \leq 4 days) of 40 mg dexamethasone or equivalent for emergency use (baseline M proteins must be drawn after this short course and prior to randomization);
 - ii) \leq 10 mg prednisone or equivalent per day;

iii) Steroid with little to no systemic absorption (ie, topical or inhaled steroids).

d) Major surgery within 4 weeks prior to randomization (kyphoplasty is not considered major surgery); subjects should have been fully recovered from any surgical related toxicities.

5. Allergies and Adverse Drug Reaction

a) Known hypersensitivity to lenalidomide, dexamethasone, any excipients in the elotuzumab formulation or recombinant protein.

6. Other Exclusion Criteria

a) Prisoners or subjects who are involuntarily incarcerated

b) Subjects who are compulsorily detained for treatment of either a psychiatric or physical (eg, infectious disease) illness.

Eligibility criteria for this study have been carefully considered to ensure the safety of the study subjects and that the results of the study can be used. It is imperative that subjects fully meet all eligibility criteria.

3.3.3 *Women of Childbearing Potential*

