4.5.3 Dose Delay or Interruption

If the dose of one drug in the regimen (ie, lenalidomide, dexamethasone or elotuzumab) is delayed or interrupted, the treatment with the other drugs may continue as scheduled. Subjects experiencing a 28-day delay in all study drugs lenalidomide, dexamethasone, and elotuzumab due to an adverse event(s) related to study treatment must be discontinued from study drug. Subjects experiencing delays unrelated to study therapy, for example due to radiation therapy may delay study treatment up to 42 days. Delays greater than 28 days must be discussed with the medical monitor.

Each cycle is 28 days. While dose delays or interruptions are permitted, the start of each cycle cannot be delayed and is fixed relative to Cycle 1 Day 1. Adjustments to the Cycle 1 Day 1 anchored schedule should not be performed. Missed doses should be skipped, not delayed, if not given within the allowed window.

Subjects may continue on study therapy even if components of the study therapy must be discontinued. For example, a subject on lenalidomide and dexamethasone may continue on study therapy even if dexamethasone must be discontinued for an adverse event. Likewise, a subject on

the investigational arm may continue on study therapy if elotuzumab must be discontinued for an adverse event or other reason. Patients are considered still on study therapy even if they continue solely on lenalidomide.

Please consult the BMS medical monitor or any questions regarding dose interruption or study therapy discontinuation.

4.5.3.1 *Elotuzumab*

In Cycle 1 and 2, an elotuzumab dose that falls outside of the pre-specified window (-1 to +3 days) must be skipped.

In Cycles 3 and beyond, elotuzumab dosing may be delayed for up to 1 week. If unable to administer within 1 week, then the dose should be skipped and resumption of the elotuzumab continues per the protocol defined schedule.

4.5.3.2 *Dexamethasone*

Dexamethasone delay should be performed as clinically indicated at the discretion of the investigator.

For subjects receiving elotuzumab, the weekly dexamethasone dose that coincides with or is temporally closest to the elotuzumab dosing must be administered as part of the premedication for elotuzumab per the guidance in [Section 4.5.1](#).

4.5.3.3 *Lenalidomide*

Lenalidomide delay should be performed as clinically indicated at the discretion of the investigator.

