Subjects should be instructed that if a dose of lenalidomide has been missed and it has been less than 12 hours since the subject's regular dosing time, to take lenalidomide as soon as the subject remembers. If it has been more than 12 hours, the dose must be skipped. Subjects should not take 2 doses at the same time.

4.5.4 *Recommended Dose Reductions*

The criteria presented in this section for dose modification are meant as general guidelines, and they are based on current US standards of clinical practice. Local standards may differ and may be followed. Dose modification may occur in the setting of lower grade toxicity if the investigator, in consultation with the Medical Monitor/Sponsor, believes that it is in the interest of subject safety.

4.5.4.1 *Elotuzumab*

No dose reduction is allowed for elotuzumab.

4.5.4.2 *Dexamethasone*

Dexamethasone dose reductions for toxicity must be performed as clinically indicated. Recommended management is described in [Table 4.5.4.2-1](#) and [Table 4.5.4.2-2](#). Deviations to the recommended dose reductions are allowed based on the clinical judgment of the investigator.

Table 4.5.4.2-1: Dexamethasone Dose Reductions

CTC AE CATEGORY	ADVERSE EVENT	TREATMENT ADJUSTMENT
Gastrointestinal	Dyspepsia, gastric or duodenal ulcer, gastritis	Treat with a proton pump inhibitor.
	Grade 1 - 2 (requiring medical management)	If symptoms persist despite above measures, decrease by one dose level.
	≥ Grade 3 (requiring hospitalization or surgery)	Hold dexamethasone until symptoms adequately controlled. Reduce by one dose level and resume along with concurrent therapy with a proton pump inhibitor. If symptoms persist despite above measures, reduce to dose level -3.
	Acute pancreatitis	Reduce to dose level -3.
Cardiovascular	Edema ≥ Grade 3 (limiting function and unresponsive to therapy or anasarca)	Use diuretics as needed, and decrease dexamethasone by one dose level. If edema persists despite above measures, decrease by another dose level.
Neurology	Confusion or Mood alteration ≥ Grade 2 (interfering with function ± interfering with activities of daily living)	Hold dexamethasone until symptoms resolve. Decrease by one dose level and resume. If symptoms persist despite above measures, decrease by another dose level.

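### Minor: first-restart lenalidomide doses are absolute with no stated cap at the current dose, and the SAP's dose levels class 20 mg as full dose

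*Protocol*

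**What the plan says.** **Who may be on a low dose.** Exclusion criterion 3 g) in Protocol 3.3.2 removes only subjects with creatinine clearance (CrCl) below "30 mL/min measured by 24-hour urine collection or estimated by the Cockcroft and Gault formula". Subjects with CrCl from 30 to below 60 mL/min are therefore eligible, and Table 4.5.4.3-3 gives them "10 mg, every 24 hours".

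**Restart after a cytopenia.** Tables 4.5.4.3-1 and 4.5.4.3-2 give these courses:
- first thrombocytopenia, or first neutropenia with other toxicity: "Resume lenalidomide at 15 mg, Days 1 - 21, once daily";
- first neutropenia as the only toxicity: "Resume lenalidomide at 25 mg, Days 1 - 21, once daily";
- each later drop: "Resume lenalidomide at 5 mg less than previous dose, Days 1 - 21, once daily", with a floor of 5 mg.

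For other Grade 3 and 4 toxicities, the end of 4.5.4.3 also uses a relative rule, the next dose level down.

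**Status of these rules.** Section 4.5.4, headed as recommended dose reductions, says: "The criteria presented in this section for dose modification are meant as general guidelines". It adds: "Local standards may differ and may be followed". Section 4.5.3 says: "Please consult the BMS medical monitor or any questions regarding dose interruption or study therapy discontinuation".

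**SAP 7.4.1.2.** A calculated lenalidomide reduction is a fall in dose level from the previous administration, derived from the actual daily dose. The levels are 0 (20.0 mg or more, labelled as the full 25 mg dose), -1 (12.5 to below 20.0), -2 (8.75 to below 12.5), -3 (6.25 to below 8.75) and -4 (below 6.25). Reasons are tabulated for calculated reductions. A by-subject listing also includes reductions reported by the investigator that do not meet the calculated rule.

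**The concern.** **Restart dose.** The rows for later drops and for other toxicities are relative, so they work from any current dose. Only the first-restart rows are absolute, and they work only for a subject who was at 25 mg, or at least above the listed dose. A site that followed them to the letter for a subject at 10 mg would raise the dose straight after a lenalidomide-related cytopenia, in some cases in a subject with reduced renal clearance of the drug.

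**Dose levels.** The protocol directs a 25 to 20 mg step: restart at 25 mg after neutropenia alone, then 5 mg less at the next drop. The SAP puts both doses in the same level. What is at stake is the accuracy of the exposure tables: the number of subjects with a reduction, the reasons for reduction and the lowest level reached.

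**Working it through.** **1. The plan's own figures.** Weekly dose = daily dose x 21 / 4.
- 25 mg: 25 x 21 / 4 = 131.25 mg/week
- 10 mg: 10 x 21 / 4 = 52.5 mg/week

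Both match the planned dose intensities in SAP 7.4.1.3. By the same formula, 15 mg is 78.75 and 20 mg is 105 mg/week.

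**2. Literal restart for a 10 mg renal subject.**
- Thrombocytopenia, or neutropenia with other toxicity: 15 / 10 = 1.5, a rise of 50% (78.75 against 52.5 mg/week if sustained)
- Neutropenia alone: 25 / 10 = 2.5, a rise of 150% (131.25 against 52.5 mg/week if sustained)

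**3. Literal restart for a non-renal subject already reduced.** Two platelet drops take a 25 mg starter to 15 mg and then to 10 mg. A first neutropenia alone then points to 25 mg, again +150%. If the earlier thrombocytopenia is held to count as other toxicity, the row gives 15 mg, still +50%. The gap is therefore not confined to renal starters.

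**4. Would the exposure tables show an escalation?** For 10 mg starters, sustained escalation gives a relative dose intensity of 150% or 250%. The top band is 90% and above, so the bands would not show it, but the maximum in the dose-intensity summary would. A short escalation can be masked. Assume 6 cycles (24 weeks), one of them at dose D, with 14 missed 10 mg doses during the interruption. Dose intensity is (5 x 210 + 21 x D - 140) / 24:
- D = 15: 1225 / 24 = 51.0 mg/week, below the planned 52.5
- D = 25: 1435 / 24 = 59.8 mg/week, above it

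The cycle count and missed doses are assumptions for illustration only.

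**5. SAP levels along the protocol's reduction paths.**

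| Path | Doses (mg) | SAP levels | Steps counted by level | Steps counted in mg |
|---|---|---|---|---|
| Repeated neutropenia alone, after the 25 mg restart | 25, 20, 15, 10, 5 | 0, 0, -1, -2, -4 | 3 of 4 | 4 of 4 |
| Repeated thrombocytopenia | 25, 15, 10, 5 | 0, -1, -2, -4 | 3 of 3 | 3 of 3 |

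The mg column applies if the SAP's reference to the dose actually received is taken to mean a comparison in milligrams. Even then, a subject whose lowest dose is 20 mg has no category in the lowest-level summary, which starts at -1 (15 mg).

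**6. Does relative dose intensity pick up 20 mg?** Sustained 20 mg is 105 / 131.25 = 80%, which falls in the tabulated 80% to below 90% band. With equal time at 25 and 20 mg and no missed doses it is (131.25 + 105) / 2 / 131.25 = 90%, which falls in the top band. The bands therefore show a long stay at 20 mg, but not always a short one.

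**The case against.** **On the restart dose.** The strongest answer is that nobody would read the rows this way. They stand under a dose-reduction heading, are recommendations, and give way to local standards. Table 4.5.4.3-3 is in the same section and depends on CrCl, not on starting status, so the natural reading is that it limits any restart. Section 1.4.5, on including subjects with renal impairment, is not in the public text, and the lenalidomide package insert goes to every site (Protocol 5.3). Either may settle the matter. This stands as a reason to expect few or no escalations. It does not remove the gap: permission to depart from a row does not say what dose to use, and a site with an explicit dose in front of it may see no question for the medical monitor. The renal table also gives no help to the non-renal subject in step 3.

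**On the dose levels.** The cut-offs are midpoints between the listed doses (20.0 between 25 and 15; 12.5 between 15 and 10), and the 25, 15, 10 and 5 mg levels match the capsule strengths supplied. The undercount depends on one reading and affects one step on one path. The by-subject listing still shows the step if the investigator reports it. All of this is correct and keeps the point small. But 20 mg can be made up as 15 + 5 mg and the protocol calls for it, and a listing does not correct a summary table.

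**Stronger readings to avoid.** A reader might infer that the protocol orders dose escalation in renal impairment, or that the trial's dose-modification reporting is unreliable. The documents support neither. The first needs the rows to be read against the heading and purpose of their section. The second overlooks that every other step is counted and that the data are also listed by subject.

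**Conclusion.** Both parts hold, as minor points.

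1. The first-restart rows lack a stated cap at the current dose. Read literally, they raise the dose of a 10 mg subject by 50% or 150%. This is a clarity gap in guidance, with actual escalation unlikely. It rests on the visible text only, and the documents do not say how many subjects would be affected.
2. Under the level-based rule, the 25 to 20 mg step is missing from the calculated-reduction count and the reason table (three of four steps counted on that path). On either reading the lowest-level summary has no place for 20 mg.

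The primary response-rate analysis, the PFS analyses and the sample size do not use these dose rules and are unaffected.

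**What to change.** **Protocol.** Add one footnote to Tables 4.5.4.3-1 and 4.5.4.3-2, for all subjects:

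> Never resume above the dose at which the toxicity occurred, or above the Table 4.5.4.3-3 dose for the current CrCl. If the listed restart dose is not below the current dose, resume at the same dose when neutropenia is the only toxicity; otherwise agree a lower dose with the medical monitor (5 mg less, not below 5 mg, consistent with the subsequent-drop rows).

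A 10 mg subject then restarts at 10 mg after neutropenia alone, and otherwise at an agreed lower dose, normally 5 mg. A 25 mg subject with CrCl of 60 mL/min or more is treated as now. Tying the cap to current CrCl also covers a 25 mg starter whose renal function falls during treatment. The cost is one footnote, notified to sites.

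**SAP 7.4.1.2.** Add a 20 mg level on the same midpoint convention:
- 0: 22.5 mg or more
- -1 (20 mg): 17.5 to below 22.5
- -2 (15 mg): 12.5 to below 17.5
- -3 (10 mg, including renal start): 8.75 to below 12.5
- -4: 6.25 to below 8.75
- -5: below 6.25

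Report the lowest level as -1 to -5. The path 25, 20, 15, 10, 5 mg then maps to 0, -1, -2, -3, -5, and all four steps count on either reading. The cost is two cut-offs in place of one, renumbered lower levels and one more category. The downside is slightly more reported reductions, and level labels that differ from the current SAP.

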4.6 Blinding/Unblinding

Not applicable.

4.7 Treatment Compliance

Starting at Cycle 1 Day 1, all treated patients will be assessed for drug compliance of all treatments administered during the course of the study. Treatment compliance will be monitored by drug accountability and recorded in the subject's medical record. For those medications taken at home (lenalidomide and dexamethasone), subjects will be provided with a medication diary in which to record study drug doses and will be instructed to bring this diary and study drug containers (lenalidomide and oral dexamethasone) to clinic visits.

4.8 Destruction of Study Drug

For this study, study drugs (those supplied by BMS or sourced by the investigator) such as partially used study drug containers, vials and syringes may be destroyed on site.

Any unused study drugs can only be destroyed after being inspected and reconciled by the responsible Study Monitor unless study drug containers must be immediately destroyed as required for safety, or to meet local regulations (eg, cytotoxics or biologics).

On-site destruction is allowed provided the following minimal standards are met:

- On-site disposal practices must not expose humans to risks from the drug.
- On-site disposal practices and procedures are in agreement with applicable laws and regulations, including any special requirements for controlled or hazardous substances.
- Written procedures for on-site disposal are available and followed. The procedures must be filed with the site's SOPs and a copy provided to BMS upon request.
- Records are maintained that allow for traceability of each container, including the date disposed of, quantity disposed, and identification of the person disposing the containers. The method of disposal, ie, incinerator, licensed sanitary landfill, or licensed waste disposal vendor must be documented.
- Accountability and disposal records are complete, up-to-date, and available for the Monitor to review throughout the clinical trial period.

If conditions for destruction cannot be met the responsible Study Monitor will make arrangements for return of study drug.

It is the study drug storage manager's responsibility to arrange for disposal of all empty containers, provided that procedures for proper disposal have been established according to applicable local, and institutional guidelines and procedures, and provided that appropriate records of disposal are kept.

4.9 Return of Study Drug

If study drug will not be destroyed upon completion or termination of the study, all unused and/or partially used study drug that was supplied by BMS must be returned to BMS. The return of study drug will be arranged by the responsible Study Monitor.

It is the study drug storage manager's responsibility to arrange for disposal of all empty containers, provided that procedures for proper disposal have been established according to applicable local, and institutional guidelines and procedures, and provided that appropriate records of disposal are kept.

Arrangements for the return of study drug will be made by the responsible Study Monitor.

5 STUDY ASSESSMENTS AND PROCEDURES

5.1 Flow Chart/Time and Events Schedule

Table 5.1-1: Screening Procedural Outline (CA204116)

Procedure	Screening Visit (-28 to -1 days of randomization)	Notes
Eligibility Assessments		
Informed Consent	X	Prior to any screening procedures
Inclusion/Exclusion Criteria	X	Within 14 days of randomization
Medical History	X	Includes date of diagnosis MM, Med Hx should be completed within 28 days of randomization
Safety Assessments		
Physical Examination	X	Include height and weight (Section 5.4.1) within 14 days of randomization
Vital Signs	X	Temperature, BP, HR, RR (Section 5.4.1) within 14 days of randomization
Performance Status (ECOG)	X	Within 14 days of randomization
Serious Adverse Events Assessment	X	Collected from the time of informed consent
Second Primary Malignancy	X	Collected from the time of informed consent (Section 6.7)
Concomitant Medications	X	Within 21 days of randomization
2-D Echocardiogram or MUGA	X	Within 28 days of randomization (Section 5.4.3)
ECG	X	Within 28 days of randomization (Section 5.4.3)
Laboratory Assessment for Safety		
CBC, differential, platelets	X	Within 14 days of randomization (Section 5.4.4)
Serum Chemistry	X	Within 14 days of randomization (Section 5.4.4)
Serum β 2-microglobulin	X	Within 14 days of randomization (assessment of ISS stage)
Serum Albumin	X	Within 14 days of randomization (assessment of ISS stage)

Table 5.1-1: Screening Procedural Outline (CA204116)

Procedure	Screening Visit (-28 to -1 days of randomization)	Notes
Urinalysis	X	Within 14 days of randomization (Section 5.4.4)
Pregnancy Test	X	For WOCBP only. 2 pregnancy tests, one 10 - 14 days prior to start of study drug and one within 24 hours prior to start of study drug. Urine tests must have a sensitivity of at least 25 IU/L.
Efficacy Assessments		
Myeloma Urine and Serum Lab tests	X	Within 28 days of randomization. Central lab analysis. (Section 5.5.2)
Bone Marrow Aspiration/Biopsy	X	Within 28 days of randomization. Bone marrow aspirate is mandatory. Bone marrow biopsy is optional. (Section 5.5.2)
Cytogenetic analysis and FISH	X	Within 28 days of randomization. Local Central lab analysis. (Section 5.5.2 and 5.7.2)
Skeletal Survey	X	Within 28 days of randomization
CT/MRI assessment for extramedullary soft tissue plasmacytoma	X	Within 28 days of randomization, if clinically indicated.
Study Drug		
Randomize	X	First dose of study drug must occur within 3 days of randomization
Dispense Study Drug	X	Those supplied by BMS or sourced by the investigator

Table 5.1-2: Short-term Procedural Outline (CA204116) Cycles 1 & 2

Procedure	Day 1	Day 8	Day 15	Day 22	Rest Days 23 - 28 ^a	Notes
Safety Assessments						
Targeted Physical Examination	X					Perform up to 3 days prior to dosing, include weight (Section 5.4.1)
Vital Signs	X	X	X	X		Measure vital signs prior to pre-medication, pre-elotuzumab infusion, 30 minutes after the start of elotuzumab infusion, at the end of infusion, and 30 and 120 minutes after the completion of infusion. Control arm measure vital signs once at each visit.
Performance Status (ECOG)	X					Evaluate prior to dosing
Serious Adverse Event Assessment	X	X	X	X		Evaluate prior to dosing
Adverse Events Assessment	X	X	X	X		Evaluate prior to dosing
Second Primary Malignancy	X					Section 6.7
Concomitant Medications	X	X	X	X		Evaluate prior to dosing
Laboratory Test for Safety						
CBC, differential, platelets	X	X	X	X		Can be drawn up to 3 days prior to study visit. (Section 5.4.4)
Serum Chemistry	X					Can be drawn up to 3 days prior to study visit. (Section 5.4.4) Serum calcium and albumin every 4 weeks from date of first dose of study drug until disease progression, even if subject is on subsequent therapy
Pregnancy Test	X	X	X	X		For WOCBP only. Urine tests must have a sensitivity of at least 25 IU/L. Weekly test within 24 hours of study medication.

Table 5.1-2: Short-term Procedural Outline (CA204116) Cycles 1 & 2

Procedure	Day 1	Day 8	Day 15	Day 22	Rest Days 23 - 28 ^a	Notes
Efficacy Assessments						
Myeloma Urine and Serum Lab Tests	Every 4 weeks from date of first dose of study drug until progression, regardless of whether patient is on study therapy or subsequent therapy.					
Day 1 of each cycle (except Cycle 1 - refer to Screening visit for defined window) until disease progression.
 
24-hour urine sample can be collected within ± 7 days of visit, and must be obtained with each cycle in all subjects who have measurable UPEP M protein (≥ 200 mg/24 hours) at baseline.
 
Subjects without measurable urine M protein at baseline and at next two subsequent cycles do not have to submit q4 week urine samples with each cycle (but must submit q12 week urine samples) until SPEP M protein becomes undetectable. In order to full fill CR/sCR criteria, both serum and urine immunofixation must be performed and be negative on two consecutive assessment. Therefore, at the time SPEP becomes undetectable, UPEP sample collection must promptly resume for these subjects, and also continue q4 weeks until SPEP becomes detectable.
 
Central lab analysis. (Section 5.5.2)

Bone Marrow Aspiration/Biopsy	For confirmation of CR/sCR if applicable or, if clinically indicated at time of suspected disease progression					Bone marrow aspirate is mandatory. Bone marrow biopsy is optional. Bone marrow samples must be assessed for clonal cells at the local lab by immunohistochemistry of the biopsy or immunofluorescence (flow cytometry) of the aspirate. Plasma cell percentage and light chain restriction assessments are required. (Section 5.5.2)
Skeletal Survey	If clinically indicated					Section 5.5.3.1
CT/MRI assessment for extramedullary soft tissue plasmacytoma	As clinically indicated and at the time of CR/sCR assessments					Section 5.5.3.2

Table 5.1-2: Short-term Procedural Outline (CA204116) Cycles 1 & 2

Procedure	Day 1	Day 8	Day 15	Day 22	Rest Days 23 - 28 ^a	Notes
Response per IMWG based criteria	Every 4 weeks from date of first dose of study drug until progression, regardless of whether patient is on study therapy or subsequent therapy.					Investigator assessment All response categories require two consecutive assessments. (Section 5.5.4)
Serum PK (Investigational arm only)	←————→					Refer to Section 5.6 for specific time points
Anti-Drug Antibody (ADA) (Investigational arm only)	←————→					Refer to Section 5.6 for specific time points
██████████	←————→					Refer to Section 5.7.1 for specific time points
Study Drug						
Premedication for Elotuzumab (Investigational arm only)	X	X	X	X		
Elotuzumab Infusion (Investigational arm only)	X	X	X	X		In Cycles 1 and 2, an elotuzumab dose that falls outside of the pre-specified window (-1 to +3 days) must be skipped.
Lenalidomide Administration	Day 1 - 21 of each cycle					
Dexamethasone Administration	X	X	X	X		
Dispense Lenalidomide	X					Dispense lenalidomide on Day 1 of cycle per the Revlimid Risk Management Plan

^a For the patients who discontinue in Cycle 1 or 2, the procedure of "End of Treatment" and "Post End of Treatment" in Table 5.1-3 must be applied.

Table 5.1-3: Long-term Procedural Outline (CA204116) Cycles 3 and Beyond

Procedure	Day 1	Day 8	Day 15	Day 22	Rest Day 23 - 28	End of Treatment	Days 30 & 60 Post End of Treatment ^a	Notes
Safety Assessments								
Targeted Physical Examination	X					X		Perform up to 3 days prior to dosing, include weight (Section 5.4.1)
Vital Signs	X		X*			X		Measure vital signs prior to administration of premedication, pre-elotuzumab infusion, 30 minutes after the start of elotuzumab infusion, at the end of infusion, and 30 minutes after the completion of elotuzumab infusion. Control arm measure vital signs once at each visit. *Not required in Cycles 19 and beyond
Performance Status (ECOG)	X					X		Evaluate prior to dosing
Serious Adverse Events Assessment	X		X*			X	X	Evaluate prior to dosing *Not required in Cycles 19 and beyond All SAEs must be collected that occur within 60 days of discontinuation of dosing
Adverse Events Assessment	X		X*			X	X	Evaluate prior to dosing *Not required in Cycles 19 and beyond
Second Primary Malignancy	X					X	X	Section 6.7 Performed at 30 and 60 day ± 1 week EOT follow up visits.
Concomitant Medications	X		X*			X	X	Evaluate prior to dosing *Not required in Cycles 19 and beyond

Table 5.1-3: Long-term Procedural Outline (CA204116) Cycles 3 and Beyond

Procedure	Day 1	Day 8	Day 15	Day 22	Rest Day 23 - 28	End of Treatment	Days 30 & 60 Post End of Treatment ^a	Notes
Laboratory Test for Safety								
CBC, differential, platelets	X					X		Can be drawn up to 3 days prior to study visit. (Section 5.4.4)
Serum Chemistry	X					X		Can be drawn up to 3 days prior to study visit. (Section 5.4.4) Serum calcium and albumin every 4 weeks from date of first dose of study drug until disease progression, even if subject is on subsequent therapy.
Pregnancy Test	X		X*			X	X	For WOCBP only. Urine tests must have a sensitivity of at least 25 IU/L. Test must be completed on Day 1 and Day 15 within 24 hours prior to dosing. WOCBP must perform a pregnancy test 90 days off treatment. This test may be performed locally if the patient is unable to return to your center. *Not required in Cycles 19 and beyond. However, patients with irregular menstrual cycles must have a pregnancy test every two weeks.

Table 5.1-3: Long-term Procedural Outline (CA204116) Cycles 3 and Beyond

Procedure	Day 1	Day 8	Day 15	Day 22	Rest Day 23 - 28	End of Treatment	Days 30 & 60 Post End of Treatment ^a	Notes	
Efficacy Assessments									
Myeloma Urine and Serum Lab Tests	Every 4 weeks from date of the first dose of study drug until progression, regardless of whether patient is on study therapy or subsequent therapy.						
Day 1 of each cycle until disease progression.
 
24-hour urine sample can be collected within ± 7 days of visit, and must be obtained with each cycle in all subjects who have measurable UPEP M protein (≥ 200 mg/24 hours) at baseline.
 
Subjects without measurable urine M protein at baseline and at next two subsequent cycles do not have to submit q4 week urine samples with each cycle (but must submit q12 week urine samples) until SPEP M protein becomes undetectable. In order to full fill CR/sCR criteria, both serum and urine immunofixation must be performed and be negative on two consecutive assessment. Therefore, at the time SPEP becomes undetectable, UPEP sample collection must promptly resume for these subjects, and also continue q4 weeks until SPEP becomes detectable.
 
Central lab analysis. (Section 5.5.2)
		
Bone Marrow Aspiration/Biopsy	For confirmation of CR/sCR if applicable or, if clinically indicated at time of suspected disease progression						
Bone marrow aspirate is mandatory. Bone marrow biopsy is optional. Bone marrow samples must be assessed for clonal cells at the local lab by immunohistochemistry of the biopsy or immunofluorescence (flow cytometry) of the aspirate. Plasma cell percentage and light chain restriction assessments are required. (Section 5.5.2)
		

Table 5.1-3: Long-term Procedural Outline (CA204116) Cycles 3 and Beyond

Procedure	Day 1	Day 8	Day 15	Day 22	Rest Day 23 - 28	End of Treatment	Days 30 & 60 Post End of Treatment ^a	Notes
Lenalidomide Administration	Day 1 - 21 of each cycle							
Dexamethasone Administration	X	X	X	X				
Dispense Lenalidomide	X							Dispense lenalidomide on Day 1 of cycle per the Revlimid Risk Management Plan

^a For subjects who discontinue study therapy before progression (eg, due to toxicity), the necessary laboratory results must be collected and the efficacy assessments must be performed until progression is confirmed even if it is beyond 60 days post end of treatment.

